## Protocol Revisions

Revision Level	Changes Made to Protocol	Date	By
0.0	Draft	13 Jul 2018	[name], [name], [name], [name]
0.1	Incorporating changes after visit to site, formatting	15 May 2019	[name], [name], [name]
1.0	n/a	12 Jul 2019	[name], [name], [name], [name]
2.0	Admin changes and clarifications based on site training visit	10 Jan 2020	[name], [name], [name]
3.0	Inclusion of OSA, clarification of endpoints, update of Figure 1, allowance for remote completion of questionnaires for visits 3 & 4, if needed, removal of visit 3a and added standard of care titration to visit 1 and 2-week acclimation period for Cohort 2, added adherence criteria for cohort 2 during acclimation period, administrative changes	10 Sep 2020	[name], [name], [name], [name]
4.0	Update medical monitor, revisions to inclusion/exclusion criteria, clarification of SAE reporting language, update to participant payment, addition of COVID-19 risk and precautions, update to Philips name/address/logo, administrative changes	09 Apr 2021	[name], [name], [name]

## II. Glossary

**Apnea:** The cessation of airflow at the nostrils and mouth for at least 10 seconds.

**Apnea/Hypopnea Index (AHI):** The number of apneas and hypopneas per hour of sleep

**Auto Adjusting Continuous Positive Airway Pressure Device:** A type of CPAP machine that monitors changes in breathing and compensates automatically by making appropriate therapeutic adjustments in pressure delivery.

**Average Volume Assured Pressure Support (AVAPS):** Positive airway pressure support that provides a gradual pressure change based on the average of the preceding several breaths

**Bi-Level PAP Therapy:** Responds to both inspiration and expiration by the patient and delivers a set amount of pressure when the patient begins spontaneous inhalation and decreasing pressure when exhalation begins

**COPD:** Chronic Obstructive Pulmonary Disease

**CPAP Pressure:** Pressure needed to maintain an open airway in a sleep apnea patient treated with CPAP, expressed in centimeters of water (cm H2O). The positive pressure can range from 4 - 25 cm H2O. Different patients require different pressures. The value is determined in a CPAP titration study.

**CPAP Therapy:** Continuous Positive Airway Pressure: Delivers a constant pressure during inspiration and expiration

**Hypersomnolence:** Excessive daytime sleepiness

**ODI:** 4% Oxygen Desaturation Index

**EFL:** Expiratory Flow Limitation: A physiological phenomenon in which an increase in driving pressure fails to result in increased expiratory flow. In patients with COPD this occurs when the external pressure driving expiration exceeds the recoil pressure holding the airways open

**EPAP:** Expiratory Positive Airway: Pressure-Physician prescribed pressure for the expiratory (breathing out) phase of an individual on Bi-level PAP therapy

**FEV1:** Forced Expiratory Volume in one second: The volume of air exhaled in the first second of the FVC maneuver and is the most reproducible measurement of airway obstruction

**FOT:** Forced Oscillation Technique: A method to detect the presence of expiratory flow limitation

**FVC:** Forced Vital Capacity: Spirometry measurement in which the patient inhales maximally and then exhales as rapidly and completely as possible

**IPAP:** Inspiratory Positive Airway Pressure: Physician prescribed pressure for the inspiratory (breathing in) phase of an individual on Bi-level PAP therapy.

**Noninvasive Positive Pressure Ventilation (NPPV):** Mechanical ventilation provided noninvasively (by mask or similar interface) rather than through an endotracheal tube or tracheostomy.

**Positive End Expiratory Pressure (PEEP):** Pressure in the lungs (alveolar pressure) above atmospheric pressure (the pressure outside of the body) that exists at the end of expiration

**OSA:** Obstructive Sleep Apnea: A disorder in which complete or partial obstruction of the airway during sleep causes loud snoring, oxyhemoglobin desaturations and frequent arousals

**S Mode:** Spontaneous Ventilation: Provides ventilation in synchrony with a person's spontaneous breathing efforts; triggering of a breath cycle is only by the patient

**S/T Mode:** Spontaneous Timed Ventilation: Provides ventilation in synchrony with a person's spontaneous breathing efforts; triggering of a breath cycle is by the patient or the ventilator, should the person fail to trigger the ventilator after a preset time. In Spontaneous/Timed mode a "backup" rate is set to ensure that the patient still receives a minimum number of breaths per minute if they fail to breathe spontaneously

**Zrs:** Total impedance of the respiratory system as measured by the forced oscillation technique (FOT) at a forcing frequency of 5 Hz

**Xrs:** The reactance (i.e. the imaginary component of the impedance) of the respiratory system as measured by the forced oscillation technique (FOT) at a forcing frequency of 5 Hz.

**ΔXrs:** The difference between the mean value of Xrs during expiration ( $\bar{X}_{exp}$ ) and the mean value of Xrs during inspiration ( $\bar{X}_{insp}$ ). A breath is classified as flow-limited if its ΔXrs is greater than 2.8 cmH2O · s · L

## Protocol Synopsis

**Title:** *Randomized Controlled Cross-Over Pilot Study of the Effectiveness of the Vector NIV Device in Hypercapnic COPD Patients with Expiratory Flow Limitation*

**Study Design:** This will be a prospective randomized controlled cross-over pilot trial to investigate the clinical efficacy and safety of the Vector A-series NIV device to treat COPD patients with chronic hypercapnia.

**Objectives:** Primary Objective: To compare treatment effect of providing NIV therapy with the Vector NIV Device vs current prescribed NIV in patients with hypercapnic COPD and evidence of expiratory flow limitation

### Secondary Objectives:

- To evaluate treatment effect of Vector on overall quality of life
- To evaluate treatment effect of Vector on sleep quality
- To evaluate treatment effect of Vector on physical activity levels
- To Evaluate treatment effect of Vector on Ventilator collected parameters
- To Evaluate treatment effect differences on nocturnal SpO2 and PaCO2 or TcCO2

**Endpoints:**Primary Endpoint:

Daytime CO2 levels at the end of 4-6 weeks of therapy as determined by Arterial Blood Gas (PaCO2)

Secondary Endpoints:

- Average daily device usage
- Therapy Comfort and Preference
- Incidence of Unanticipated Serious Adverse Device Effects (USADEs) and Serious Adverse Events (SAEs) for the Vector vs. the control group.

Exploratory Endpoints:

- Changes in quality of life scores ((CAT) SGRQ, dyspnea ratings mMRC),
- Ventilator collected parameter differences after 6 weeks of use (Respiratory Rate (RR), Minute Ventilation (MV))
- Sleep Quality differences as measured by PSG and actigraphy
- Changes in activity levels (mean and max activity counts)

**Study Population:** Approximately 30 COPD patients with chronic hypercapnia and evidence of expiratory flow limitation will be included.  
**Phase:** Pilot study

**Sites/Facilities Enrolling Participants:** Temple University Hospital

**Description of Study Intervention:** NIV with Auto Adjusting EPAP

**Study Duration:** Approximately 12 months

**Participant Duration:** Approximately 15 weeks

### III. Background Information

Chronic Obstructive Pulmonary Disease (COPD) is a major cause of morbidity and mortality worldwide.

Treatment options for COPD patients consist of medications, such as bronchodilators and anti-inflammatory drugs, pulmonary rehabilitation, long-term oxygen therapy (LTOT), and lung transplantation. Studies have shown that bronchodilators and anti-inflammatory drugs show minor or no benefit on long term outcomes but rather are used mainly for symptomatic relief. Pulmonary rehabilitation has been demonstrated to improve functional status and symptoms but there is sparse evidence on long term outcomes of this therapy. Lung transplantation is only appropriate for a small number of patients; therefore, there is no demonstration of improved long-term survival rate.

Of these available therapies, few have been shown to significantly improve long-term patient outcomes. For the severe COPD patient, LTOT is the only treatment that demonstrated prolonged survival in controlled studies. But, despite the effectiveness of LTOT, COPD is still characterized by a high morbidity and mortality rate.

Noninvasive positive pressure ventilation (NPPV) is one therapy that may prove beneficial to stable COPD patients. NPPV, also known as NIV, is the use of positive pressure ventilation administered via a nasal or full-face mask (that covers both the nose and mouth). This type of ventilation has become a well-established and increasingly used therapeutic option for patients with hypercapnic respiratory failure (HRF) due to COPD.

NPPV, used nocturnally, may improve nighttime hypoventilation that is common with COPD patients. An improvement in nocturnal hypoventilation would reset the respiratory center sensitivity for CO2. This would result in an improvement in daytime gas exchange and sleep quality. It is also known that hyperinflation in patients with COPD increases their work of breathing, thus fatiguing the respiratory muscles. It has been suggested that by applying nocturnal NPPV it would allow the respiratory muscles to rest, resulting in muscle function recovery, increased respiratory muscle strength, reduced the tendency for fatigue and improvement in pulmonary function and gas exchange. Adverse effects of NPPV are usually minor and manageable. The masks may cause some discomfort and air pressure and flow have adverse effects. All adverse effects encountered, including mask discomfort, nasal or mouth congestion or dryness, eye irritation, gastric insufflation, and nasal bridge ulceration will be recorded on data sheets that are part of the case report form.

COPD is a disease that results in varying degrees of dyspnea, or shortness of breath. Spirometry is a method of diagnosing COPD with the diagnosis confirmed by presence

of a post bronchodilator  $FEV_1 < 80\%$  of the predicted value in combination with an  $FEV_1 / FVC < 70\%$ .

The presence of airflow obstruction has been identified as one of the main causes of dyspnea in patients with chronic obstructive pulmonary disease . Expiratory Flow Limitation (EFL) occurs when the driving pressure outside the airways exceeds the recoil pressure holding the airway open. As airflow obstruction worsens, EFL appears at much lower flows for a given lung volume and it becomes present at rest or at least develops early during exercise .

Previously detection of EFL consisted of either invasive esophageal balloon or relatively complex plethysmographic techniques. An alternative approach, and one that will be used in this study, involves the Forced Oscillation Technique (FOT), which is now incorporated into the vector device.

In 2003, *Dellacà et al.* proposed a new method to detect EFL during quiet breathing non-invasively using the FOT. It was based on the observation that COPD patients with EFL developed large negative swings in the respiratory system input reactance measured at 5Hz during expiration. They used this observation to define a sensitive and specific method of determining the presence of EFL. Normally the reactance reflects the elastic and inertial properties of the respiratory system but when flow limitation is present, the oscillatory signal cannot pass through the choke points and reach the alveoli. This produces a marked reduction in the apparent compliance and, consequently, a fall in  $X_{rs}$ .

Although this  $X_{rs}$  reduction is present at all the frequencies, the greatest difference is seen at the lowest frequency. Since the quiet breathing signal can interfere with the estimation of  $Z_{rs}$  at frequencies below 5 Hz, this frequency was used for the forcing signal. The difference between the mean value of  $X_{rs}$  during inspiration ( $\bar{X}_{insp}$ ) and  $\bar{X}_{exp}$  is called  $\Delta\bar{X}_{rs}$ . A breath is classified as flow-limited if its  $X_{exp, min}$  is greater than  $2.8 \text{ cmH}_2\text{O} \cdot \text{s} \cdot \text{L}^{-1}$ .

This technology has been evaluated in numerous clinical studies for both the detection, reduction and abolishment of expiratory flow limitation in patients with COPD. In 1956, Dubios et al, demonstrated the FOT method to be applicable to the measurement of airway resistance in patients, evaluation of therapeutic procedures designed to relieve airway obstruction, separation of airway resistance from tissue resistance, and study of the multiple factors that may affect airway resistance. And in additional work in 2006,

[figure not shown]
Dellaca et al, suggested the forced oscillation technique may be useful in chronic obstructive pulmonary disease patients using nasal pressure support by identifying expiratory positive airway pressure levels that support breathing without increasing lung volume, as turn increase the work of breathing and reduce muscle effectiveness and efficiency.

The Vector project has incorporated this method as a new feature into the Philips BiPAP Ventilator overall platform (K121623). The device has been designed to produce a 5 Hz sine wave with peak to peak amplitude of approximately 2 cm H2O superimposed upon the pressure and flow generated by the device. The resultant feedback waveform is then filtered and analyzed to measure reactance (deltaX) and thus determine if EFL is present. Subsequently, in a bi-level ventilation mode the EPAP (and concurrently and proportionally the IPAP keeping pressure support unchanged) is increased until the EFL is essentially abolished (falls below the predetermined EFL threshold). Since this reactance is analyzed continuously (breath by breath) during both inspiration and expiration, it is relatively immune to external factors such as modest leaks or coughing / swallowing.

## **A. Description of the Intervention Studied**

### Study Device Description:

The Vector ventilator (i.e. BiPAP A-40 EFL) with Vector Algorithm, Philips, Inc., Murrysville, PA) is intended to provide non-invasive ventilatory support to treat adult patients with Respiratory Insufficiency with the primary cause being COPD. It is intended to be used within the home, institutional/hospital, and diagnostic laboratory environments. This device is not intended for life support. It can be used to screen for the presence, and abolishment of Expiratory Flow Limitation. Study devices will be packaged and tracked according to lot number, serial number, and/or manufacturing number, as applicable.

#### **IV. Study Design Rationale**

##### **A. Study Objectives and Purpose**

###### **Primary Objective**

To compare treatment effect of providing NIV therapy with the Vector NIV Device versus current prescribed NIV in patients with hypercapnic COPD and evidence of expiratory flow limitation

###### **Secondary Objectives**

- To evaluate treatment effect of Vector on Ventilator collected parameters
- To evaluate patient comfort and therapy preference
- Incidence of Unanticipated Serious Adverse Device Effects (USADEs) and Serious Adverse Events (SAEs) for the Vector vs. the control group.

###### **Exploratory Objectives**

- To evaluate treatment effect of Vector on overall quality of life
- To evaluate treatment effect of Vector on sleep quality
- To evaluate treatment effect of Vector on physical activity levels
- To evaluate treatment effect differences on nocturnal SpO2 and PaCO2 or TcCO2

###### **Study Hypothesis:**

We hypothesize in patients with hypercapnic COPD, NIV therapy provided by the Vector device, with an optimized automatically adjusting EPAP to abolish expiratory flow

limitation, will maintain equal levels of gas exchange (PaCO2) will provide patients with improved therapy comfort and adherence when compared to standard NIV.

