### **Withdrawal:**

The term “discontinuation” refers to the participant’s premature withdrawal from the study prior to completing all procedures. Participants may be discontinued from the study for any of the following reasons:

- If in the investigator’s judgement, continuation in the study may prove harmful to the participant. Such a decision may be precipitated by adverse events, including fever, nausea, rash, changes in vital signs, or the development of a new medical

condition. The investigator will be solely responsible for making medical/safety decisions regarding the participant's continued participation in the study.

- Noncompliance;
- At the request of the participant.
- Further admission with AECOPD as the primary diagnosis

The study team will document whether or not each participant completed the study. If, for any participant, study treatment or assessments were discontinued, the reason will be recorded.

For the naïve NIV patient cohort, participants will be allowed to keep the device until a marketed device can be provided to them through normal commercial distribution pathways.

The study goal is to have 30 participants successfully complete the study. It is estimated that 50 patients may need to be enrolled in order to complete 30

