## **XI. Statistical Methods**

### **Determination of Sample Size**

No power analysis was performed to determine the sample size for this pilot study. The results of this study may be used to power a larger pivotal trial.

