### **General Considerations**

The primary analysis will be performed including all consented participants. Descriptive data tables will be provided for all variables of interest. Continuous data will be presented by mean, standard deviation, median, minimum, and maximum observation. Data will be presented in the untransformed and transformed format (if applicable) for each continuous variable. Categorical data will be presented as frequencies and percentages. All formal statistical analyses will be performed using either SAS® or SPSS® software. Significance tests will be conducted at a two-sided significance level of  $p < 0.05$ .

There are no statistical criteria for terminating the study. No sensitivity analysis will be completed, and any deviations to the original statistical plan will be noted in the analysis report.

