## **Primary Analysis**

Since this was a crossover study, the endpoints were compared between the two therapies as paired samples. For each continuous endpoint, the paired differences will be examined for normality using the Shapiro-Wilk and Kolmogorov-Smirnov tests, and if the distribution does not deviate significantly from normality, the treatment effect will be examined using a paired t-test; otherwise, the endpoint was examined using the non-parametric Wilcoxon Signed-Ranks test. Categorical data will be evaluated using the McNemar Test.

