## **Interim Analysis**

Since this is a pilot study, descriptive statistics may be reviewed as the study is ongoing, but formal statistical comparisons will be performed after the study is completed.

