## **XVII. Registration on ClinicalTrials.gov or other applicable registry**

This trial will be registered on Clinical Trials.gov. It is the intent that these data may be used for to support regulatory clearance and/or consideration for a submission to peer review publication.

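### The hypothesis predicts equal PaCO2, but the only planned inference is a two-sided test of difference, which can reject equality and never support it

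*Combined protocol and SAP*

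**What the plan says.** The Study Hypothesis in Section IV.A predicts that Vector "will maintain equal levels of gas exchange", names PaCO2 as the measure, and predicts better comfort and adherence than standard NIV. Daytime PaCO2 by arterial blood gas after 4–6 weeks is the primary endpoint. The Primary Objective in the same section is neutral: "To compare treatment effect of providing NIV therapy with the Vector NIV Device versus current prescribed NIV".

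In Section XI, Primary Analysis, if the paired differences pass normality checks, "the treatment effect will be examined using a paired t-test"; otherwise the Wilcoxon signed-ranks test is used. General Considerations adds: "Significance tests will be conducted at a two-sided significance level of" 0.05. The descriptive output listed there for continuous data is mean, SD, median, minimum and maximum. Determination of Sample Size says: "No power analysis was performed to determine the sample size for this pilot study". The target appears under Withdrawal in Section VI: "The study goal is to have 30 participants successfully complete the study".

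No margin, equivalence or non-inferiority rule, or confidence interval appears anywhere in the documents, and nothing says what p above 0.05 would mean for PaCO2.

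**The concern.** The null hypothesis of the planned test is the state of affairs that the sponsor predicts. Failing to reject it is not evidence for it. A small or noisy trial fails to reject more often, and so would seem to confirm the hypothesis more often than a large, precise one.

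With equality in the hypothesis and no rule for reading the result, a non-significant PaCO2 comparison could be reported as maintained gas exchange when the data are also compatible with a worsening of 2 mmHg or more. This goes beyond internal use: Section XVII says "these data may be used for to support regulatory clearance" or a peer-reviewed publication, and Section XI says the results may be used to power a pivotal trial. Those uses need the size of the difference and its precision, and the plan does not promise an interval.

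**Working it through.** **Inputs from the documents.** 30 completers, so 30 pairs and 29 degrees of freedom (Section VI, Withdrawal); paired t-test (Section XI, Primary Analysis); two-sided 0.05 (Section XI, General Considerations). With no power analysis, there is no planned figure to reproduce.

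**Assumptions.** The documents give neither an SD of the paired PaCO2 differences nor a difference that matters clinically. I take SDs of 4, 6 and 8 mmHg and true differences (Vector minus standard of care) of 2, 3 and 4 mmHg. These are illustrative.

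**Step 1: behaviour when the hypothesis is true.** At a true difference of 0, P(p > 0.05) = 0.95 for any n, whether 5, 30, 100 or 1000 pairs. More data add no support for equality. At a true 3 mmHg difference with SD 8, the chance of non-significance is 90% with 5 pairs, 49% with 30 and 4% with 100.

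**Step 2: precision with 30 pairs.** Half-width of the 95% interval = t(0.975, 29) × SD/√30 = 2.045 × SD/5.477 = 0.3734 × SD.

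- SD 4: 1.49 mmHg
- SD 6: 2.24 mmHg
- SD 8: 2.99 mmHg

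For example, with an observed SD of 6 and an observed mean difference of +2.0 mmHg, the interval is 2.0 ± 2.24, or −0.24 to 4.24. The test is non-significant, yet the data are compatible with a worsening of about 4 mmHg.

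**Step 3: chance of a non-significant test when Vector is truly worse.** Noncentral t with 29 df and noncentrality δ√30/SD; P(p > 0.05) = P(−2.045 < T < 2.045). For δ = 2 and SD = 6 the noncentrality is 2 × 5.477/6 = 1.826, which gives 57.7%.

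| True difference | SD 4 | SD 6 | SD 8 |
|---|---|---|---|
| 2 mmHg | 24.6% | 57.7% | 73.7% |
| 3 mmHg | 2.2% | 24.6% | 49.0% |
| 4 mmHg | <0.1% | 5.8% | 24.6% |

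**Step 4: what 30 pairs could support if a margin were set.** True difference 0; margins of 3 and 4 mmHg for illustration only. The maintained rule requires the upper limit of the two-sided 95% interval to lie below the margin (noncentral t). The equal rule requires both limits to lie within ± the margin (numerical integration over the sample SD, checked by simulation).

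| Rule and margin | SD 4 | SD 6 | SD 8 |
|---|---|---|---|
| Maintained, 3 mmHg: power | 97.8% | 75.4% | 51.0% |
| Maintained, 4 mmHg: power | >99% | 94.2% | 75.4% |
| Equal, 3 mmHg: power | 95.5% | 50.8% | 9.4% |
| Equal, 4 mmHg: power | 99.9% | 88.3% | 50.8% |
| Equal, 3 mmHg: pairs for 80% power | 21 | 44 | 77 |
| Equal, 4 mmHg: pairs for 80% power | 13 | 26 | 44 |

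**The case against.** The strongest reply is that this is a declared, unpowered pilot with a neutral primary objective that a paired comparison serves. Nothing in the plan says that p above 0.05 will be read as equality, and the hypothesis is a loosely worded narrative sentence, not a formal null and alternative. Section XI also plans descriptive tables, and a reader given the mean and SD of the paired differences could work out the interval.

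Much of this stands. The mismatch lies between the hypothesis sentence and Section XI, the harm depends on a misreading, and pilot status lowers the severity. But the plan still schedules formal significance tests on its primary endpoint, and nothing in it prevents the misreading. An interval can be derived only if the SD of the differences, or the test statistic with the mean difference, is reported. The plan does not promise that, and SDs by treatment are not enough.

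Two objections to the numbers are fair but do not change the conclusion. First, the SD range is a choice: at SD 10 the chance of missing a 3 mmHg difference is 64.5%, so the risk is not confined to 2 mmHg. Second, requiring 95% limits for the equal rule is stricter than the usual two one-sided tests at 5% each, which use a 90% interval. On that basis the pairs for 80% power fall to 17, 36 and 63 (margin 3 mmHg) or 11, 21 and 36 (margin 4 mmHg). Thirty pairs may still be too few.

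**Conclusion.** The concern holds. The only inference planned for PaCO2 can contradict the stated hypothesis but cannot support it, and this follows from the form of the test without any assumed number. The practical size depends on an SD that the documents do not give. For SDs of 4 to 8 mmHg and 30 pairs, a misleading null is mainly a risk for true differences of about 2 mmHg at SD 6–8 (58–74%). It is below 50% at 3 mmHg within that range and small at SD 4. The comfort and adherence parts of the hypothesis predict improvement, and difference tests suit them. This should be fixed; given the pilot status it does not undermine the trial.

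**What to change.** 1. In Section XI, Primary Analysis, make the primary result the mean paired PaCO2 difference (Vector minus standard of care) with its two-sided 95% confidence interval. If the Wilcoxon route is taken, report the Hodges–Lehmann estimate with its 95% interval.
2. Add a sentence: a p-value above 0.05 will not be interpreted as evidence of equal PaCO2.
3. As the default, replace the equality wording in the Study Hypothesis with an aim to estimate the PaCO2 difference and its precision. Keep the difference tests for comfort and usage.
4. If the sponsor prefers to keep a claim, fix and justify a margin before anyone sees PaCO2 summaries by treatment. The Interim Analysis section says "descriptive statistics may be reviewed as the study is ongoing" and does not exclude summaries by treatment. Conclude maintained only if the upper 95% limit is below the margin, and equal only if both limits lie within ± the margin. If a 90% interval is preferred for the equal rule, say so in advance.

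Items 1–3 cost wording and one interval, with no extra patients, visits or procedures. Item 4 may cost patients: under the assumptions above, the equal rule needs from 13 to 77 pairs for 80% power, against the 30 targeted. The 3 and 4 mmHg margins are illustrations, not recommendations.
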